Independent DSMB: An independent DSMB, which will be guided by a signed charter, will perform ongoing review of blinded and unblinded data, including both safety and cases of COVID-19 at scheduled data review meetings and at 3 planned interim analyses.

In addition to blinded and unblinded review of safety data, at each data review meeting the DSMB will review any confirmed COVID-19 cases amongst the participants, which may inform of any increased risk of vaccine associated enhanced respiratory disease. Further details are described in the DSMB Charter.

At each analysis, the DSMB will review the available data and make recommendations to the Sponsor to continue, modify, or discontinue study enrollment (if the study is enrolling). The DSMB will also review safety and, if available, immunogenicity data at each interim analysis.

For dose selection for Phase 3 study use, it is expected that the Sponsor will select the dose on the basis of review of available immunogenicity data and safety data (including DSMB evaluation of the benefit/risk profile). It is anticipated that if one or more vaccine groups have an acceptable safety and immunogenicity profile, the vaccine group with the fewest number of doses will be selected for future use based on the review of the Phase 2 study data.

Study Vaccine, Dosage, and Route of Administration:

The ARCT-021, ARCT-154, and ARCT-165 study vaccines are lipid nanoparticle formulated ribonucleic acid (RNA) products. The RNA comprises a replicon based upon Venezuela equine encephalitis virus (VEEV) in which RNA coding for the virus structural proteins has been replaced with RNA coding for the SARS CoV-2 full-length spike glycoprotein.

ARCT-021 is based on the unmodified spike protein of the SARS-CoV-2 Wuhan strain.

ARCT-154 and ARCT-165 are based on prefusion-stabilized presentations of the spike protein of the Wuhan strain containing the D614G mutation and variant of concern B.1.351 SARS-CoV-2 strains, respectively.

For LUNAR-COV19 vaccines, the nanoparticle composition includes 4 lipid excipients (ionizable cationic lipid, ATX-126; neutral lipid, 1,2-distearoyl-sn-glycero-3-phosphocholine (DSPC); cholesterol; and polyethylene glycol-lipid conjugate (PEG2000-DMG).

ARCT-021, given as 2 priming doses administered on Day 0 and Day 28, will use the frozen liquid formulation.

Arcturus Therapeutics, Inc.
Protocol ARCT-021-04, Version 6.0

ARCT-021
09 March 2022

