4.2.2 Discontinuation of Study Vaccine (Participant)

Additional administrations of study vaccine are absolutely contraindicated for any of the following reasons:

- Grade 3 solicited AEs (as confirmed by Investigator review), severe anaphylaxis, severe related (possibly, probably, or definitely) unsolicited AEs, or immediate type hypersensitivity (≤ 4 hours after injection) following the administration of the study vaccine.
- Any SAE judged to be related (possibly, probably, or definitely) to vaccine.
- Pregnancy in a female participant.
- Any clinically significant medical condition that, in the opinion of the Investigator, poses an additional risk to the participant if he/she continues to participate in the study.
- New information becomes available that makes further participation unsafe.

Arcturus Therapeutics, Inc.
Protocol ARCT-021-04, Version 6.0

ARCT-021
09 March 2022

A participant should not receive subsequent administrations of study vaccine for any of the following additional reasons:

- Participant receives an off-study COVID-19 vaccine
- Participant is lost to follow-up.
- As deemed necessary by the Investigator for non-compliance or other reasons. This may include previously undisclosed or new conditions that meet exclusion criteria.
- Termination of the trial.

If any of these events occur during the study, then the participant must not receive additional doses of study vaccine. Furthermore, the participant will be encouraged to continue study participation for safety and immunogenicity evaluations through the Early Termination Visit after the first vaccination.

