7.1 Estimands and Intercurrent Events

Possible intercurrent events are presented in [Table 7-1](#).

Table 7-1 Intercurrent Event Types

Label	Intercurrent Event (IcEv) Type
IcEv1 (Death)	Death due to any cause (including pneumonia) other than COVID-19.
IcEv2 (Missed dose)	Does not receive the second or booster vaccinations at Day 28 and Day 208, respectively.
IcEv3 (Immune-modifying)	Use of immune-modifying drugs or non-study vaccines which interfere with immunogenicity.
IcEv4 (Early infection)	Antigens or antibodies indicating exposure to SARS-CoV-2 prior to vaccination or early infection before Day 7. (This IcEv is particularly relevant to assessing immunogenicity.)
IcEv5 (Study infection)	Develops COVID-19 or asymptomatic SARS-CoV-2 infection on or after Day 7. (This IcEv is particularly relevant to immunogenicity and CESI events.)

Attributes for the primary safety and immunogenicity estimands with strategies for intercurrent events (IcEvs) are presented in [Table 7-2](#).

Table 7-2 Primary Safety and Immunogenicity Estimands With Rationale and Strategies to Address Intercurrent Events

Estimand Label	Estimand 1 (Safety)
Estimand Description	Count and percentage of vaccinated healthy adults who would develop MAAEs, NOCDs, SAEs, AEs leading to discontinuation/withdrawal, solicited AEs, and unsolicited AEs: These will be evaluated after each dose of study vaccine by priming vaccine study group (Group 1, 2, 3, and 4) and by booster vaccine received (ARCT-021, ARCT-154, ARCT-165, or placebo). A treatment policy strategy is used for assessing safety irrespective of an early infection within 7 days after the first vaccination or an infection during the study or missed subsequent vaccination. Infections and death are included in the endpoint (composite strategy).
Target Population	Participants receiving at least 1 dose of study vaccine (as defined by eligibility criteria).
Endpoint	Occurrence of MAAEs, NOCDs, AEs leading to discontinuation/withdrawal, SAEs, solicited, or unsolicited AEs: 
 Solicited AEs within 7 days of each vaccination (by Toxicity Grade, Appendix 13.4): Day 7, Day 35, Day 215 Unsolicited AEs within 28 days of each vaccination (by mild/moderate/severe severity): Day 28, Day 56, Day 236 MAAEs, NOCDs, SAEs, AEs leading to discontinuation/withdrawal from Vaccination 1 to Prior to Vaccination 2, Vaccination 2 to Prior to Booster Vaccination, Overall Prior to Booster Vaccination, and Post-booster Vaccination

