4.5. Treatment Misallocation

In a blinded fashion, it was determined that there are 4 scenarios observed for 5 participants in the final data with treatment misallocation where the vaccine combination/sequence received differs from the randomized treatment group:

Randomized Treatment Group (Priming Vaccination)	Treatment Misallocation Details	Treatment Group to be Used for Safety Set and Reactogenicity Set for Priming Vaccination
7.5 µg ARCT-021 Single Dose	Non-placebo received at Dose 2	7.5 µg ARCT-021 Two Dose
7.5 µg ARCT-021 Two Dose	Placebo received at Dose 2	7.5 µg ARCT-021 Single Dose
5.0 µg ARCT-021 Two Dose	Placebo received at Dose 2	7.5 µg ARCT-021 Single Dose
7.5 µg ARCT-021 Single Dose	Placebo received at Dose 1*	Placebo

* Note that it was confirmed placebo was received at Dose 2 as planned.

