8.2.2. Supportive Analyses of Primary and Secondary Immunogenicity Endpoints

8.2.2.1. Supportive Analyses of Estimand 2

To assess the magnitudes of the differences between the treatment groups (ARCT-021 vs. Placebo) in SARS-CoV-2 neutralizing antibody (NAbs) and SARS-CoV-2 binding antibody (BAbs) endpoints, an analysis of covariance (ANCOVA) model will be fitted to the natural log transformed neutralizing antibody titers measured against SARS CoV 2 with terms for treatment group, age group (≥ 18 to < 56 and ≥ 56 years) (stratification factor at randomization) and natural log baseline titer by each post-vaccination immunogenicity visit. No imputation of missing data will be done.

The geometric least squares mean (GLSM) and corresponding 2-sided 95% CI for the antibody titers for each treatment group will be provided by visit. The GLSM and corresponding 95% CI results in log-transformed scale estimated from the model will be back-transformed to obtain these estimates in the original scale. Geometric mean ratio (GMR), estimated by the ratio of GLSM and the corresponding 2-sided 95% CI will be provided to assess the treatment difference between ARCT-021 group vs. placebo group at each visit.

ANCOVA analyses will be performed for the priming vaccination period on mITT analysis set only.

8.2.2.2. Supportive Analyses of Estimand 3

The common difference of seropositivity and seroconversion rates and 95% CIs between each vaccine dose group and the placebo will be estimated using the Miettinen-Nurminen method with age group (≥ 18 to < 56 and ≥ 56 years) as stratification factor for each time point.

Miettinen-Nurminen analyses will be performed for the priming vaccination period on mITT analysis set only.

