13.5. Appendix 3: Estimands and Intercurrent Events

Possible intercurrent events are presented in the table below.

Table 13-3 **Intercurrent Event Types**

Label	Intercurrent Event Type
IcEv1 (Death)	Death due to any cause (including pneumonia) other than COVID-19.
IcEv2 (Missed dose)	Does not receive the second vaccination at Day 28 where second vaccination assigned was ARCT-021 or does not receive booster vaccination at Day 208 where booster vaccination assigned was active ARCT booster. It is not necessary to exclude placebo missed second doses as there is no impact.
IcEv3 (Immune-modifying)	Use of immune-modifying drugs or non-study vaccines which interfere with immunogenicity. Immune-modifying drugs will be determined from a medical review of medications taken during the study.
IcEv4 (Early infection)	
Priming vaccination period: Antigens or antibodies indicating exposure to SARS-CoV-2 prior to vaccination or early infection before Day 7. (This IcEv is particularly relevant to assessing immunogenicity.) Early infection is defined as follows:
 
 ○ Positive PCR saliva test at baseline OR ○ Positive PCR test at any time up to 7 days post-baseline OR ○ Positive SARS-CoV-2 baseline serostatus 
Booster vaccination period: Antigens or antibodies indicating exposure to SARS-CoV-2 prior to vaccination or early infection before Day 7 post booster vaccination. (This IcEv is particularly relevant to assessing immunogenicity.) Early infection for different boosters is defined as follows:
 
 ○ Positive PCR saliva test on Day 208 OR the booster vaccination OR ○ Positive PCR test at any time up to 7 days post-booster vaccination
IcEv5 (Study infection)	Develops COVID-19 or asymptomatic SARS-CoV-2 infection on or after Day 7. (This IcEv is particularly relevant to immunogenicity and CESI events.). Study infection is defined as COVID-19 infection recorded on the adverse event CRF page with start date on or after Day 7. The following AE preferred terms will be considered: Asymptomatic COVID-19, COVID-19, Suspected COVID-19. Positive MSD nucleocapsid antibody value of 5000 AU/mL or higher at any point after baseline (with start date on or after Day 7) will also be considered as on-study infection.

Attributes for the primary safety estimands with strategies for IcEvs are presented in Table 13-4 below.

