Estimand Label	Estimand 2 (Geometric Mean Titers/Concentrations)
Estimand Description	
The GMT of NAbs (primary) and BAbs (secondary) against SARS-CoV-2 up to Early Termination after first vaccination with ARCT-021 of each group (5.0, 7.5 µg, or placebo) and with/without booster dose in healthy adults.
 
Interest will lie in comparing the GMT of each dosing regimen to placebo based on the Geometric Mean Ratio (GMR).
 
The hypothetical strategy is used to estimate antibody levels had all scheduled vaccinations been received, and without subsequent SARS-CoV-2 infection or influence from immune-modifying drugs or non-study vaccines. The principal stratum strategy excludes those with active or early SARS-CoV-2 infection within 7 days after the first study vaccine administration.

Analysis Population	Vaccinated healthy adults (as defined by eligibility criteria) without active or early SARS-CoV-2 infection (infection within 7 days after the first vaccination).
Endpoint	Total NAbs (primary) and BAbs (secondary) specific for the SARS-CoV-2 measured pre- and post-priming vaccine administration (on Day 0, 14, 28, 42, 56, and 208) and following booster vaccine administration (Day 236, Early Termination).
Treatment Conditions	Placebo or 5.0 µg or 7.5 µg ARCT-021 administered on Day 0, Day 28; placebo, ARCT-021, ARCT-154, or ARCT-165 administered on Day 208.
Population-Level Summary	The GMT and GMR of comparisons of interest at each time point. GMR will compare responses in placebo-, ARCT-021-, ARCT-154-, and ARCT-165-vaccinated groups at relevant timepoints. For additional considerations on population-level summary see the SAP.
Intercurrent Event Strategy	
IcEv1 (Death)	Hypothetical strategy
IcEv2 (Missed dose)	Hypothetical strategy
IcEv3 (Immune-modifying)	Hypothetical strategy
IcEv4 (Early infection)	Principal stratum strategy (based on study phase)
IcEv5 (Study infection)	Hypothetical strategy
Rationale for Strategies	Hypothetical strategy is used to understand antibody levels achieved through receiving scheduled vaccination, without subsequent SARS-CoV-2 infection and without any influence from immune-modifying drugs or non-study vaccines. In estimation, the hypothetical uses a statistical model on the mITT (excluding data points following intercurrent events and not complete removal of all data for the participant).

Estimand Label	Estimand 3 (Rise/Seroconversion)

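### The SAP drops antibody values after a missed ARCT-021 Dose 2 and has no model to stand in for them, so post-Day 28 results in Groups 2 and 3 are complete-case estimates of a hypothetical estimand

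*SAP*

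**What the plan says.** **The target.** SAP Appendix 3 (Table 13-5) gives Estimands 2 and 3 a hypothetical strategy for a missed dose. They describe antibody levels and seroconversion as if all scheduled vaccinations had taken place. Both rationales say a statistical model on the mITT set will be used, "excluding data points following intercurrent events and not complete removal of all data for the participant".

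**The trigger.** Protocol 7.1 defines the missed-dose event (IcEv2) for every group: "Does not receive the second or booster vaccinations at Day 28 and Day 208, respectively". SAP Table 13-3 narrows the Dose 2 part to "Does not receive the second vaccination at Day 28 where second vaccination assigned was ARCT-021", and adds "It is not necessary to exclude placebo missed second doses as there is no impact". SAP Section 11, which lists changes from the protocol, does not mention this.

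**The estimators.** Table 13-6 and SAP 8.2.1 give GMT, GMFR and response rates visit by visit, with t-based or Clopper-Pearson intervals. The supportive titre model (SAP 8.2.2.1) is a separate ANCOVA at each visit with treatment, age group and log baseline titre: "No imputation of missing data will be done". Rate differences use a by-visit stratified Miettinen-Nurminen method.

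**Who is stopped.** Protocol 4.2.2 bars further study vaccine after, among other events, "Grade 3 solicited AEs (as confirmed by Investigator review". The Synopsis defines study vaccine to include placebo, so the bar applies in all four groups. Barred participants are encouraged to keep giving immunogenicity samples.

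**Known dosing errors.** SAP 4.5 lists four scenarios in five participants. In one, the assignment was 7.5 µg single dose but placebo was given at Dose 1; the footnote adds "Note that it was confirmed placebo was received at Dose 2 as planned". The mITT set is analysed as assigned (SAP 4.4.3).

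**The concern.** A hypothetical estimand needs something to stand in for the values that are set aside. A raw GMT at Day 56 in Groups 2 and 3 simply averages those who received Dose 2. The by-visit ANCOVA adjusts only for Day 0 titre, which should carry little information about vaccine response once participants with baseline infection or positive serostatus are excluded (IcEv4). The Day 14 and Day 28 titres of stopped participants, which reflect their own response to Dose 1, are collected and kept but do not inform any later visit.

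Meanwhile, participants barred for the same kind of Dose 1 reaction keep their later values in Groups 1 and 4. Groups 1 and 3 share the same first dose (7.5 µg), so after Day 28 they differ in whom they include as well as in regimen.

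The results exposed are the Day 42, 56 and 208 GMTs, GMFRs and seroconversion rates in Groups 2 and 3, and their comparisons with placebo. Responses 28 days after each priming dose also serve the dose and schedule objective (SAP Table 2-1), so Day 56 is directly involved.

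**Working it through.** **Inputs from the documents.** 75 participants per group per age cohort, so 150 per group (SAP 4.2). Geometric CV 180%, SD 1.2 on the natural-log scale; check: √ln(1 + 1.8²) = √ln 4.24 = 1.20, which agrees.

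**Assumed inputs.** The documents give no Grade 3 rate after Dose 1 and no titre difference for those stopped. Let *g* be the share of Group 2 or 3 whose later values are dropped, and *k* their titre excess in SDs. The nearest documented figure is 8 AEs leading to discontinuation among more than 500 ARCT-021 recipients (Protocol 1.5): 8/500 = 1.6% at most. It counts AEs across trials and is not the rate needed. I use *g* from 1.6% to 20%.

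**Step 1: effect on the GMT.** Dropping a share *g* whose mean log titre is *k* × 1.2 higher multiplies the GMT by exp(−*g* × *k* × 1.2). IcEv2 leaves the placebo GMT untouched, so the GMR to placebo moves by the same factor.

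| *g* | *k* = 0 | *k* = 0.5 | *k* = 1 |
|---|---|---|---|
| 1.6% | 1.00 | 0.990 | 0.981 |
| 5% | 1.00 | 0.970 | 0.942 |
| 10% | 1.00 | 0.942 | 0.887 |
| 20% | 1.00 | 0.887 | 0.787 |

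The understatement runs from 1% to 21%. A negative *k* would reverse the direction. For scale, the 95% CI half-width factor of a 150:150 GMR is exp(1.96 × 1.2 × √(2/150)) = 1.31.

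**Step 2: would the earlier titres help?** Simulation of Group 3 against Group 1, 150 each, true GMR 1, Day 28 to Day 56 correlation 0.7 (assumed), 4,000 replicates. Those stopped have the same excess at both visits.

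| *g*, *k* | Deletion in Group 3 only | Deletion in both groups | Group 3 fit using Day 28 titre |
|---|---|---|---|
| 1.6%, 0.5 | 0.992 | 1.001 | 0.998 |
| 10%, 0.5 | 0.939 | 0.996 | 0.979 |
| 20%, 1 | 0.785 | 0.998 | 0.928 |

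Using the Day 28 titre removes about two thirds of the bias on the log scale. In the last row, ln 0.928 / ln 0.785 = 0.0747 / 0.2421 = 0.31, so 31% remains. It would remove nearly all of it only if stopping depended on the observed titre alone. In fact stopping depends on reactions.

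**Step 3: dosing errors.** A participant given placebo twice but analysed as 7.5 µg single dose would be expected to sit near LLOQ/2 = 7.843/2 = 3.92 IU/mL. One such person in 150 multiplies the Group 1 GMT by (3.92/GMT)^(1/150). For an assumed GMT of 50 to 300 IU/mL this is 0.983 to 0.971, a fall of 1.7% to 2.9%. SAP 4.5 does not say whether the row holds one participant or two. For those assigned ARCT-021 who received placebo at Dose 2, the IcEv2 wording does not settle whether they received the second vaccination.

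**The case against.** Several counter-arguments have force.

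- **The carve-out is sound.** A missed saline injection should not alter titre, so Group 1 and Group 4 values stay on target. This stands. A reader might infer that those values should be deleted too; the estimand does not support that.
- **The Phase 3 choice is not at risk.** The Synopsis says "the vaccine group with the fewest number of doses will be selected for future use" if safety and immunogenicity are acceptable, and a reader might infer that this choice receives a biased comparison. It does not. Protocol 7.8 and the Synopsis record that a single 5 µg dose had been selected by protocol version 4.0, and this SAP governs the final analysis only. A single 5 µg dose matches Group 2 before its second dose, and IcEv2 removes nothing there.
- **The specified contrasts are with placebo.** Two-dose against single-dose GMT ratios are not planned, and Protocol 7.2 states there is no hypothesis testing. This stands, but the placebo ratios for Groups 2 and 3 carry the same shift.
- **The per-protocol set is a check.** It requires the correct assigned doses, so it excludes missed and wrong doses in every group, and its GMT tables are planned (SAP 8.4). This stands in part: ANCOVA and rate differences are mITT only, and the per-protocol set describes those who completed dosing, not the hypothetical target.
- **Participants are not removed from Groups 2 and 3.** Correct: their Day 0, 14 and 28 values remain.
- **The study ended early and sensitivity analyses were removed** (Protocol 13.5.8), and SAP Section 1 warns of limited interpretation beyond Day 56. This limits how much extra work is justified.

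**Conclusion.** The concern holds as a mismatch between estimand and estimator. After Day 28, Groups 2 and 3 get a complete-case estimate where the SAP promises a modelled hypothetical one, and informative titres already in hand go unused. Estimand 3 has the same gap. The bias is zero if stopped participants have the same titres as others. It is about 1% to 2% at the nearest documented stopping figure, and up to 21% at the far end of the assumed range. Rate, size and direction are all assumptions; a reader might infer that two-dose regimens are shown to look weaker, but the documents do not establish this.

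The dosing-error gap is small, at roughly 2% to 3% per never-vaccinated participant under the stated assumptions. It acts on Group 1. In a Group 1 against Group 3 reading it would partly offset a downward bias in Group 3, which is no reason to leave either in place.

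The consequence is for the final report of the primary immunogenicity and dose/schedule objectives. This is a cheap improvement and does not invalidate the analysis.

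**What to change.** 1. Add a supportive repeated-measures model for log titres at Days 14, 28, 42, 56 and 208, with treatment by visit, age group and log baseline, and with post-event values set to missing. Report GMT and GMR from it. If placebo values are degenerate at LLOQ/2, use a simpler covariance or fit the ARCT-021 groups alone. Date it and label it as added after the interim analyses, since SAP Section 10 shares unblinded interim data with the sponsor. State that it reduces the bias without removing it.
2. Beside it, show Day 42 and Day 56 GMTs with no deletion for a missed Dose 2, described as a different estimand. Adding seroconversion rates to this display would give Estimand 3 a comparable check.
3. Extend IcEv2 to the SAP 4.5 dosing errors, from the first wrong dose that changes active exposure.
4. List the narrowing of the protocol's IcEv2 definition in SAP Section 11. Restate the exclusion rule in SAP 8.2.1; at present the SAP's analysis sections spell it out only for CMI (8.3.2).

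**Cost:** SAP wording, one extra model per assay and one display. No new data are needed. The model relies on a missing-at-random assumption, which should be stated with the results.

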6.1 Evaluation of Participants With Suspected COVID-19

If a participant experiences any of the following potential symptom of COVID-19 (irrespective of perceived etiology or clinical significance), he or she is instructed to contact the site immediately: fever, chills, cough, shortness of breath or difficulty breathing, fatigue, muscle or body aches, headache, new loss of taste or smell, sore throat, congestion or runny nose, nausea or vomiting, and diarrhea.

If the symptoms are confirmed, an Unscheduled Visit should occur. An exception to this rule is if the potential symptoms of COVID-19 are observed within 7 days following first study vaccine administration. Individuals with COVID-19 diagnosed prior to 7 days after first study vaccination will not be required to attend for an unscheduled visit but will be followed clinically for resolution/stabilization in accordance with local practice.

As shown in [Figure 6-1](#), for all other participants evaluated on the basis of clinical symptoms or risk of exposure as assessed at least 7 days after first vaccination, the Unscheduled Visit will be performed at the site (preferred) or via telemedicine visit within 48 hours of symptom onset or identified exposure, and saliva (or nasal swab or nasal turbinate swab) will be collected for testing for SARS-CoV-2 by RT-PCR. Repeat sample collection for SARS-CoV-2 should be performed within 120 hours of onset of symptoms if symptoms persist and the first SARS-CoV-2 test was negative. In addition to the saliva/nasal swab collection, visit procedures will include interview, physical examination, vital signs, pulse oximetry and body temperature measurement, and blood sampling for testing of N antibody to SARS-CoV-2. In the event the visit is performed via telemedicine, the physical examination, vital signs, and blood sampling for testing of N antibody to SARS-CoV-2 will not be required. Participants will be provided with a pulse oximeter, which, along with the previously provided thermometer, will be used to perform daily measurements. **Please note: samples of blood (for binding antibody test for nucleocapsid) and saliva (for RT-PCR testing) sent to the central laboratory are not regarded as diagnostic tests.** Therefore, if clinical suspicion of COVID-19/SARS-CoV-2 exposure exists, local laboratory testing should be performed and/or arrange with a primary care provider as clinically warranted to appropriately manage the care of the participant.

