6.4.1.1.7 Clinical Events of Special Interest

Clinical Events of Special Interest (CESI) are events relating to the detection of disease (SARS-CoV-2) activity relevant to the study vaccine. These events are analyzed separately from safety data; however, if the CESI demonstrates untoward signs or symptoms that, in the opinion of the Investigator, suggest the events are more likely related to study vaccine rather than to SARS-CoV-2, these signs/symptoms will be reported as AEs.

To be considered as a CESI of COVID-19 the following case definition adapted from the CBER Guidance: Development and Licensure of Vaccines to Prevent COVID-19 ([DHHS 2020](#)) must be met:

- The participant must have experienced at least 1 of the following systemic symptoms: fever ($\geq 38^{\circ}\text{C}$), chills, myalgia, headache, sore throat, congestion or runny nose, nausea or vomiting, diarrhea, fatigue, new olfactory and taste disorder(s), cough, shortness of breath, or difficulty breathing OR
- Clinical or radiographical evidence of pneumonia; AND
- The participant must have at least 1 test positive for SARS-CoV-2 by RT-PCR.

To be considered as a CESI of asymptomatic SARS-CoV-2 infection, a participant who demonstrates none of the COVID-19 symptoms described above but who tests positive for SARS-CoV-2 on PCR test or anti-nucleocapsid antibody test (if nucleocapsid antibody negative prior to entry into the study) will be counted.

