6.4.1.3.3 Exceptions

Because CESI events are typically associated with the disease under study, they will not be reported as SUSARs even though the event may meet the definition of a SAE. These events will be recorded on the CESI eCRF page in the participant's eCRF.

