6.1. Demographics

Descriptive statistics will be calculated for the following continuous demographic and baseline characteristics: age (years), weight (kg), height (cm), body mass index (BMI) (kg/m²). The number and percentage of participants will be provided for categorical variables such as age group, sex, race, ethnicity, country, site, baseline SARS-CoV-2 serostatus (positive/negative/missing) defined by nucleocapsid testing at Day 0, and evidence of viral shedding as measured by a saliva RT-PCR test at Baseline.

Baseline SARS-CoV-2 serostatus is defined as SARS CoV-2 nucleocapsid (N) antibody level of greater or equal to 5000 (AU/mL). This threshold is defined by BioA laboratories based on levels for a clinical definition of PCR-confirmed COVID-19 infection.

The number and percentage of participants will be summarized by site and by stratification factor at randomization (i.e., ≥ 18 to <56 years; ≥ 56 years) separately based on the Safety set for the priming vaccination period, re-enroll subjects, and booster vaccination period.

Summaries will be provided separately based on the Safety set, mITT set, PP set, mITT-CMI subset by study treatment group. The summaries will be repeated by study treatment group for re-enrolled subjects based on Safety set and for the booster vaccination period based on the Booster Safety set, Booster mITT set, Booster PP set, Booster mITT-CMI subset. Summary of demographics by ≥ 18 to <65 years vs. ≥ 65 years will also be provided for the priming vaccination period.

For screened failure participants, age (years), gender, race and ethnicity will be presented in a listing.

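### The study-infection rule (IcEv5) does not read RT-PCR or the CESI page, and the priming early-infection rule (IcEv4) does not read reported cases, so an infected participant can stay in Estimands 2 and 3

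*SAP*

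**What the plan says.** SAP Appendix 3, Table 13-3 gives the working definitions.

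- **IcEv4, priming period.** The triggers are a positive baseline saliva PCR, "Positive PCR test at any time up to 7 days post-baseline", or "Positive SARS-CoV-2 baseline serostatus". SAP 6.1 sets the serostatus cut-off at N antibody of 5000 AU/mL or more.
- **IcEv4, booster period.** PCR only: at Day 208 or the booster, or within 7 days after it.
- **IcEv5.** "Study infection is defined as COVID-19 infection recorded on the adverse event CRF page with start date on or after Day 7". Three preferred terms count, including Suspected COVID-19. An N value of 5000 AU/mL or more after baseline, dated Day 7 or later, also counts.

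Under SAP Tables 13-5 and 13-6, IcEv4 removes the participant (principal stratum) and IcEv5 removes later data points (hypothetical strategy).

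The protocol's own definition of infection is wider. Section 6.4.1.1.7 counts as asymptomatic infection a participant without symptoms "who tests positive for SARS-CoV-2 on PCR test or anti-nucleocapsid antibody test". The schedules of events place saliva RT-PCR at Days 0, 7, 14, 28, 35, 42 and 56, at the booster-period clinic visits, at unscheduled visits and at early termination.

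The documents differ on recording. SAP 9.1 says these infections are entered as adverse events, and then also refers to the CESI page. Protocol 6.4.1.3.3 says "These events will be recorded on the CESI eCRF page in the participant's eCRF", and 6.4.2 has sites report them by completing the CESI form. Section 6.4.1.1.7 has signs and symptoms reported as AEs only when the investigator thinks them more likely due to vaccine. Section 6.1 says central-laboratory saliva results are not diagnostic.

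For the first week, Protocol 6.1 says: "Individuals with COVID-19 diagnosed prior to 7 days after first study vaccination will not be required to attend for an unscheduled visit".

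**The concern.** The two rules serve one purpose, to keep infection-driven antibody out of Estimands 2 and 3, but they read different evidence on either side of Day 7. Before Day 7 a swab counts and a reported case does not. After Day 7 a reported case counts and a swab does not.

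A missed infection matters most in the placebo group. Placebo titres are expected near the imputed floor, and placebo is both the denominator of the GMR and the reference for the seroconversion differences. A missed infection there pulls the vaccine-placebo contrast towards no effect. In a vaccine group it inflates the response. Either way the estimate departs from the stated estimand.

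**Working it through.** **Step 1. What each rule reads (SAP Table 13-3).**

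| Evidence | IcEv4 priming | IcEv4 booster | IcEv5 |
|---|---|---|---|
| Positive RT-PCR | yes, through Day 7 | yes, at Day 208/booster and through 7 days after | no |
| AE-page case | no | no | yes, start on Day 7 or later |
| CESI-page case | no | no | no |
| N at or above 5000 AU/mL | at baseline | no | after baseline, dated Day 7 or later |

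**Step 2. Which infections escape.** Take five windows (Days 1-6, Day 7, Days 8-207, 0-7 days after the booster, more than 7 days after the booster). Cross them with the seven non-empty combinations of positive PCR, AE-page record and later N at or above 5000 AU/mL. That gives 5 × 7 = 35 patterns. Neither rule catches three of them:

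- Days 1-6: AE-page record only.
- Days 8-207: positive PCR only.
- More than 7 days after the booster: positive PCR only.

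A case recorded only on the CESI page behaves as if it had no AE record.

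**Step 3. Day 7.** A positive PCR on Day 7 triggers IcEv4. If the case is also on the AE page with a Day 7 start, it triggers IcEv5 too. The consequences differ: the whole participant is removed, or only later data. Nobody escapes here. Because the first antibody draw after baseline is Day 14, the practical difference is mainly whether the baseline value is kept.

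**Step 4. Illustrative size.** The documents give neither the number missed nor the titres, so there is no plan figure to reproduce. Inputs:

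- Neutralization LLOQ 7.8431 IU/mL (SAP 8.2.1), with values below it set to half (SAP 4.6): 7.8431/2 = 3.92 IU/mL.
- Placebo n = 75 per age cohort × 2 = 150 (SAP 4.2).
- Assumed: all other placebo participants sit at 3.92, and k missed infections have titre T of 50, 200 or 1000 IU/mL.

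Placebo GMT factor = (T/3.92)^(k/n). For k = 1, n = 150:

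- T = 50: 12.75^(1/150) = 1.017
- T = 200: 51.0^(1/150) = 1.027
- T = 1000: 255^(1/150) = 1.038

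With no missed infection in the vaccine group, the unadjusted GMR is multiplied by 1/1.017 = 0.983 down to 1/1.038 = 0.964. Placebo seroconversion rises by 1/150 = 0.7 points. For k = 5 the GMT factors are 1.089, 1.140 and 1.203. A given k weighs more wherever n is smaller, as in one age cohort.

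For scale, with the planning SD of 1.2 on the natural-log scale and 150 per group, the 95% interval for the GMR is about ×/÷ exp(1.96 × 1.2 × √(2/150)) = exp(0.272) = 1.31.

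**The case against.** The best defence is that the AE page is the SAP's source of record. SAP 9.1 sends confirmed and asymptomatic infections there, IcEv5 lists a preferred term for asymptomatic COVID-19, SAP 9.4 tabulates incidence from that page, and the SAP prevails over the protocol where methods differ. Protocol 6.4.1.1.4 also treats COVID-19 assessed at an unscheduled visit as a medically attended event, to be reported on the AE page. Recording on the CESI page does not preclude AE entry as well.

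Much of this stands for symptomatic cases. It does not cover an asymptomatic positive at a scheduled visit, which involves no unscheduled visit and comes from a test called non-diagnostic. The precedence clause governs analysis method and cannot change what sites recorded. SAP Version 5 followed a June 2022 data review, after the 16 February 2022 target for last visits.

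The N criterion is a real backstop. N and neutralizing antibody come from the same scheduled draws, so anyone who reaches 5000 AU/mL is caught. It is incomplete because SAP 6.1 ties the cut-off to clinically defined, PCR-confirmed COVID-19, and asymptomatic infections may not reach it.

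The Days 1-6 gap is narrow. A reader might infer that the protocol leaves such cases unswabbed. It waives only the unscheduled visit; Day 7 saliva RT-PCR is scheduled for everyone with a zero-day window, and the second IcEv4 trigger is not limited to saliva. A reader might also infer a matching gap for cases reported in the first week after the booster. There is none, because an AE-page start date then is already past study Day 7 and IcEv5 catches it.

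**Conclusion.** The mismatch is real. The main exposure is a positive RT-PCR after Day 7, or more than 7 days after the booster, with no AE entry and N below 5000 AU/mL. The lesser one is a case reported on Days 1-6 with no positive PCR through Day 7 and N below 5000 AU/mL afterwards.

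It is tempting to conclude that infected participants do remain and that the GMR is biased by a known amount. The documents support neither. They show that the rules allow it; they give no count of discordant cases and no titres. The 2-4% rise in placebo GMT per missed infection rests on the assumed titres and on every other placebo participant sitting at LLOQ/2. It is small against the expected width of the GMR interval, and the study tests no hypothesis. This is therefore a cheap improvement to the match between estimand and estimator, and no evidence that the results are wrong.

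**What to change.** In SAP Table 13-3:

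1. Add to IcEv5 any positive SARS-CoV-2 RT-PCR, central or local, and any CESI-page case. Apply the same addition after the booster.
2. Add to priming IcEv4 any AE- or CESI-page case with onset before Day 7.
3. Keep the existing preferred terms, including Suspected COVID-19, and the N criterion. Limiting the AE route to confirmed cases would drop infections that IcEv5 now reads.
4. Derive one earliest infection date per participant and split it once at Day 7, so that each infection falls under one rule. The IcEv labels already place Day 7 with IcEv5; align the PCR wording of IcEv4 with them. State how imputed AE onset dates are handled, because the rules in SAP 13.4 can move a partial date to the day of first vaccination.
5. Reconcile SAP 9.1 with Protocol 6.4.1.3.3 on where these cases are recorded.

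The cost is one table edit and one derived variable from data already collected. The downside is that a few more samples are excluded. A count of participants whose status changes would show whether the gap mattered.
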